- Subjects will meet Rome IV criteria for functional nausea, irritable bowel syndrome, dyspepsia or functional abdominal pain as determined by a pediatric gastroenterologist
- Patients must have an intact external ear that is free of infection or severe dermatological conditions, have stable vital signs for their respective age, no history of seizures and no currently implanted electrical device

Exclusion Criteria:

- Mental retardation or pervasive developmental disorder or epilepsy
- Psychosis
- Genetic or chromosomal disorders
- Pregnancy
- Subjects who admit to substance abuse during screening
- Patients with findings of peptic ulcer disease, H.pylori gastritis, celiac disease, inflammatory bowel disease, allergic disorders, or any chronic condition or medication that may cause nausea or pain
- Patients who are treated with opioids or who had any changes in their medical regimen in the past four weeks prior to study
- Patients with a history of allergy to adhesives

Study Design Overview

Subjects will undergo medical workup per standard of care. Subjects refractory to current medical therapy may be enrolled without changes to their current medical treatment. No new pharmacological agents will be added during the 4-week study period and no changes in dosing or scheduling of current therapy will be allowed during the study period. Subjects will be screened weekly for any side effects by registered nurses who are part of the Pediatric Translational Research Unit (pTRU). All subjects will be asked to notify the PI or research team with any worsening in symptoms or side effects of therapy. If symptoms worsen or fail to improve during the study or if their clinical presentation changes in any way, subjects will have the option to drop out any time, receive standard medical therapy and appropriate referrals. If per standard of care, a subject requires a change in one or several of their regular medications during the study, they will be asked to notify the research team. To monitor this, the subjects will be inquired about their medication list and doses during their weekly visits. If the medication change is determined to potentially affect the study results, the subject may be excluded from further study as determined by the PI.

Protocol and Procedures

Pre (Baseline):

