The primary investigator, a co-investigator or research coordinator will introduce the study to eligible patients seen in the CHW Autonomic and Gastroenterology Clinic during their regularly scheduled clinic visit or while

admitted to the hospital (at the end of admit). A member of the research team will explain the details and purpose of the study during an informed consent discussion. Once the patient and caregivers have had enough time to consider participation, understand all of the risks and benefits and would like to participate, they will complete the informed consent, assent and HIPAA documents.

Medical and psychological history will be obtained to verify eligibility and screen patients for alcohol, nicotine, and drug abuse following the completion of consent/assent documents. All eligible subjects will complete the questionnaires related to demographic and the Functional Disability Inventory (FDI). This will take about 5-10 minutes total to complete.

Visit 1 and 4: Subjects will undergo blood drawn for mitochondrial bioenergetics and have EAD placed. HRV will be measured before EAD placement at visit 1 and after EAD placement at visit 4. This visit will take about 60 min. They will complete the FDI again

Visit 2; 3: EAD will be changed and a new one will be placed.

Visit 5: This visit is about 2-3 month after the last EAD has been removed. At this visit they will undergo again blood drawn for mitochondrial bioenergetics, measurement of HRV and complete FDI.

The samples will be processed and stored in the laboratory of study research team members, [name] in Health Research Center, H5720.

E. TOTAL NUMBER OF HUMAN RESEARCH PARTICIPANTS PROPOSED FOR THIS STUDY AT THIS SITE AND GLOBALLY. WHAT ARE THESE NUMBERS BASED ON?

7 patients aged 12-18 years, who are being evaluated in the Gastroenterology or FGID clinic are eligible to participate in the FGID group.

F. DRUGS OR PROCEDURES

Table 1.

	Pre	Visit 1	Visit 2	Visit 3	Visit 4	Visit 5
Screening & Consent	x					
Heart Rate Variability		x			x	x
FDI	x				x	x
EAD		x	x	x	x	
Mitochondrial bioenergetics		x			x	x

All procedures will be performed in the Children's Hospital of Wisconsin (CHW) Pediatric Translational Research Unit (pTRU).

Measurements and Data Collection

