At the time of each EAD placement, a member of the research team will inquire and document current medications and doses and if subjects experienced any side effects from the EAD during the previous week. Subjects will also be asked if they wore the device for all five days and it will be documented if the device was returned to the research team.

Demographic Information

Data will be collected as part of the clinic visit and at enrollment. This includes child's date of birth, age, sex, ethnicity, and caretaker marital status. The physician assessment will also include questions about prior medical diagnoses, co-morbid symptoms and the characteristics of pain and nausea such as timing and triggers. The FDI will be performed at visit 1; 4 and 5. This instrument has demonstrated reliability and validity and have been used for both clinical and research purposes in pediatric populations.

Medical Information

Information recorded for patients is part of clinical care and includes weight, height, vital signs, medications, gastrointestinal symptoms, early life events, family history, surgeries and other medical co-morbidities.

[figure not shown]
Heart Rate Variability

HRV reflects the variability of the R-R interval in the electrocardiogram and its frequency domains (30). HRV is an indirect measure of central autonomic control and an indicator of overall psychological well-being (31). Reductions in resting HRV reflect decreases in vagal output. The high frequency range of HRV is considered representative of vagal (parasympathetic) activity and studies show altered vagal tone as measured by HRV in subjects experiencing nausea (32). All subjects will undergo a 10 minute baseline HRV measurement (five minutes supine and 5 standing) after 10 minutes of rest. Recordings will be performed supine and standing to assess baroreflex response. HRV indices such as high and low frequency domains, low/high frequency ratio and the time domain RMSSD as a surrogate of vagal tone (30) will be analyzed using Kubios software. The RMSSD values will be the primary HRV outcome and compared to baseline (pre-EAD stimulation), post-stimulation and 2-3 month later at follow up.

We will use the following HRV collection methods; *eMotion* Faros ECG Mobile 360 and the Actiwave by CamNTech. The *eMotion* Faros will primarily used, and in the event that the faros devices are not available, the Actiwave will be available as a backup device.

eMotion Faros ECG Mobile 360

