4. The subject will be advised not to immerse the device in water as the device is water resistant but not water proof. If showering or washing their hair, subjects will be instructed to place a dry wash cloth or plastic such as Press n' seal over the area to help protect the device. Subjects will be given a contact person (primary investigator and research coordinator) to call if they are having any problems with the device or if it falls off.
5. The patient will be instructed on removing the device after 5 days. If not comfortable doing so or unable to carry out the instructions, the patient may be seen that day for removal by one of the investigators.
6. The patient will be asked to return the used device for proper disposal when they return for their follow-up appointment.
7. The subject will be given a handout with information (attached) on device handling, exact date and time of device removal and date and time to return.
8. The subject will be advised to refrain from using any new or as needed anti-emetic or pain medications.
9. The subject is dismissed.

G. RISK CATEGORY

45 CFR 46.405- Research involving greater than minimal risk but presenting the prospect of direct benefit to the individual child subjects involved in the research.

H. RISKS AND THE PRECAUTIONS WHICH WILL BE TAKEN TO MINIMIZE RISK EXPOSURE

Safety Data

All safety variables (e.g., adverse events will be summarized for each assessment time (including follow-up) using descriptive statistics. Incidence of adverse events will be summarized by treatment.

Heart Rate Variability:

Participants will be asked in advance if they have a history of skin allergy to adhesives to avoid provoking any skin irritation or rash. However, some redness from the adhesive on the ECG surface electrodes may temporarily appear.

Neuro-stimulation:

Overall risks/ discomforts involved are very minimal – Rare (event rate 1% - < 5%)

Possible risks/discomforts may involve:

- a. Discomfort upon insertion of the electrodes for < 5 minutes - Rare (event rate 1% - < 5%)
- b. Discomfort at the lead placement site > 5 minutes – Rare (1 % - < 5%)
- c. Bleeding at the electrode site if the neurovascular bundle is penetrated - Rare (event rate 1% - < 5%)
- d. Localized discomfort if the electrodes should become dislodged during the wearing of the device - Rare (event rate 1% - < 5%)
- e. Localized dermatitis - Rare (event rate 1% - < 5%)
- f. Drop in blood pressure - Rare (event rate 1% - < 5%)

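### Current treatment is to stay unchanged, yet subjects are advised at device placement to refrain from as-needed anti-emetic and pain drugs, so as-needed use can shift just as stimulation starts

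*Combined protocol and SAP*

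**What the plan says.** Section D, Study Design Overview, sets the general rule. On entry: "Subjects refractory to current medical therapy may be enrolled without changes to their current medical treatment". For the 4-week study period it rules out new drugs and adds that "no changes in dosing or scheduling of current therapy will be allowed during the study period". The same section then provides for changes that become necessary: "If per standard of care, a subject requires a change in one or several of their regular medications during the study", the research team is to be told, and the principal investigator may exclude the subject if the change could affect the results.

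The exclusion criteria in section D remove "Patients who are treated with opioids or who had any changes in their medical regimen in the past four weeks prior to study". They do not mention non-opioid anti-emetics or analgesics taken as needed.

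Section F, EAD placement details, item 8, is one step in the list carried out when a device is fitted: "The subject will be advised to refrain from using any new or as needed anti-emetic or pain medications". It carries no start date, end date or exception.

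On recording, Measurements and Data Collection in section F says that at each placement "a member of the research team will inquire and document current medications and doses". The Study Design Overview describes a similar question at the weekly visits. Neither place mentions as-needed use.

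**The concern.** The general rule keeps treatment as it was at entry. Item 8 asks for a change from entry in anyone who already takes an anti-emetic or pain drug as needed. The plan does not say which statement governs that subject.

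Timing makes this a statistical matter. If as-needed use falls on the day the first device is fitted, two things change at once between Visit 1 and Visit 4. Any effect of the second on RMSSD (the primary HRV outcome), hfHRV, FDI, bioenergetics or cytokines would be counted as an effect of stimulation. On the safety side, nausea or pain that worsens after a subject refrains from a drug could be misread as a device side effect or as failure of the device.

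**Working it through.** The plan gives no figure to reproduce here. The check sets its statements side by side and follows their order in time.

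1. **Do the two statements overlap?** Item 8 names new drugs and as-needed drugs as separate things. The part on new drugs agrees with the Study Design Overview. The part on as-needed drugs naturally reaches drugs the subject already has. Whether these belong to current therapy is not stated, because the term is not defined.
   - If they do, following item 8 alters current therapy, and both statements cannot be followed.
   - If current therapy means regular drugs only, both can be followed, but as-needed use still changes under item 8.

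2. **Can such a subject be enrolled?** Yes. Of medication-related exclusions that bear on this, only opioid treatment and a regimen change in the prior four weeks are listed. The population has painful functional gastrointestinal disorders, and functional nausea is among the qualifying diagnoses.

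3. **When does item 8 first apply?** At the first placement, which is at Visit 1: "Subjects will undergo blood drawn for mitochondrial bioenergetics and have EAD placed". For HRV the order is explicit: "HRV will be measured before EAD placement at visit 1 and after EAD placement at visit 4". Baseline HRV therefore precedes the advice and Visit 4 HRV follows it. No statement in the text restricts as-needed drugs before Visit 1.

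4. **When does it end?** Not stated. The general rule covers the 4-week study period. Visit 5 comes about 2 to 3 months after the last device is removed, and its blood draw, HRV and FDI fall under no stated rule on as-needed drugs.

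5. **Can the analysis separate the two changes?** No. There are 7 subjects, no control arm is described, and the Statistical Analysis section compares Visits 1, 4 and 5 without naming medication as a covariate or a basis for display.

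6. **How many subjects?** The documents do not say how many take such a drug. The possible range is 0 to 7 of 7. Each subject is 1/7 = 14% of the data.

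**The case against.** The strongest reply is that the two statements form one coherent rule: keep regular drugs constant and take nothing new or as needed. An as-needed drug has no fixed schedule to alter, and the Study Design Overview itself speaks of regular medications when it deals with necessary changes. This reading is possible, so a reader should not treat a strict contradiction as proven. It does not remove the timing problem, because a subject who used a drug as needed before Visit 1 and follows item 8 afterwards has still changed use on the day stimulation began.

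Other replies stand in part.

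- Item 8 is advice. It does not show that any subject stops a drug. A subject must have such a drug, have used it around Visit 1, and then follow the advice.
- Earlier instruction cannot be ruled out, since the handout mentioned in item 7 and the consent pages are not in the available text. The protocol text itself does not place the advice earlier.
- A reader might infer that as-needed use goes unrecorded. The documents do not support that: a question about medications and doses does not exclude as-needed drugs. What is unspecified is the number of doses actually taken.
- A reader might infer that a subject who worsens can only drop out. That is also unsupported. Dropping out is offered as an option, worsening is to be reported to the team, and standard-of-care changes to regular drugs are allowed with notification and review by the principal investigator. That provision, however, covers changes a subject needs; it does not cover one the protocol itself advises.
- An uncontrolled pilot of 7 cannot attribute its changes to the device in any case. True, but this is a co-intervention that the plan itself introduces, and it can be avoided.

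**Conclusion.** The concern holds in conditional form. The two statements conflict for a subject whose current treatment includes a non-opioid as-needed anti-emetic or pain drug, if current therapy includes such drugs. On either reading of that term, the text does not apply item 8 before baseline or say when it ends, so a change in as-needed use can coincide with the start of stimulation and cannot be separated from it in the Visit 1 to Visit 4 comparison.

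The size is unknown: 0 to 7 of 7 subjects, at 14% of the data each. The documents give no basis for a narrower range, and none for the direction or size of any bias in the outcomes. The conclusion assumes that at least one enrolled subject uses such a drug, that use before Visit 1 is not restricted by instructions outside the available text, and that the advice is followed at least in part. It should be put right, because as-needed use not recorded at Visit 1 cannot be reliably reconstructed later.

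**What to change.** 1. Reconcile the Study Design Overview with item 8 of the EAD placement details. State whether current therapy includes as-needed drugs. Let one rule on as-needed anti-emetic and pain drugs apply from before the Visit 1 baseline measurements through Visit 4, and state what applies from then to Visit 5. Which rule it is remains for the investigators to decide.
2. Add to the existing medication enquiry the as-needed drug, the number of doses in the past 7 days, and the time of the last dose before HRV and blood draw. Begin at Visit 1 before those measurements, and include Visit 5, which the enquiry at device placement does not reach.
3. List each subject's Visit 1 to Visit 4 changes and flag those whose as-needed use changed. With 7 subjects a listing is more useful than a subgroup comparison, which could leave one or two subjects in a group.

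The cost is a reconciled rule in the text, three fields on an enquiry already in use, and one flag in a listing. No visits are added; the only burden is a few more questions at each one.

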We and others have documented that subjects with functional gastrointestinal disorders (FGID) have decreased vagal tone. A cross sectional meta-analysis of 11 articles of adult subjects with IBS (8) showed decreased vagal modulation with increased sympathetic tone. Low vagal modulatory activity occurs in other chronic pain conditions (9-13), and has been linked with poor adaptive behavior in a meta-analysis of 44 studies in 5000 children (14). In turn, poor adaptability and high pain severity in childhood more likely results in pain-related FGID, non-abdominal chronic pain, and co-morbid anxiety and depression in adulthood (15). We have also shown that the mitochondrial bioenergetics is decreased in children and adolescents with FGID and other comorbid conditions. [name] has also demonstrated in a recently accepted manuscript to *The Lancet Gastroenterology & Hepatology* that 4 weeks of auricular neuro-stimulation with an Electro Auricular Device (EAD) improves pain and functionality. We have also demonstrated that this is done through improvement in vagal tone by measuring heart rate variability (HRV) before and after EAD. In this proposal we would like to see if improving vagal modulation through a 4-week of neuro-stimulation with the EAD results in increase in mitochondrial bioenergetics and decrease in inflammatory markers.

B. SPECIFIC AIMS / HYPOTHESIS

Specific aim: determine if vagal stimulation through an electro auricular device (EAD) will improve mitochondrial bioenergetics and decrease inflammation.

Hypothesis: The vagal nerve modulates mitochondrial bioenergetics capacity through muscarinic cholinergic M2 receptors. Therefore, knowing that the mitochondrial bioenergetics is decreased in adolescents with FGID, we postulate that a 4 week neuro-stimulation with an EAD that has already shown to increase vagal tone will produce an increase in mitochondrial bioenergetics in this patient group. Furthermore, the vagus plays a critical role in the anti-inflammatory pathways, therefore increasing vagal tone should also decrease the inflammatory response.

C. BACKGROUND, SIGNIFICANCE, AND RATIONALE

Pediatric FGIDs (pFGIDs) are prevalent (16, 17) and disabling. For example IBS, just one of many pFGIDs, occurs in 6-15% of the pediatric population (18) and affects daily activity in 40% of the children (19). Chronic pain affects approximately 8.8 million children annually, with a cost of 11.8 billion, with about 1/3 of this burden

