Subjects will enter a 4-week, prospective treatment trial with the FDA-approved and commercially available EAD manufactured by Key Electronics (Jeffersonville, IN, USA) and distributed by Innovative Health Solutions (Versailles, IN, USA). The device is cleared under the PZR Class II (substantially equivalent, generic device) classification, with intended as a percutaneous nerve stimulator for substance use disorders determined by the states. EAD is an ambulatory, neurological device which consists of a battery powered, externally affixed generator with 4 wire leads attached to 3 electrode/ needle arrays and one single point needle. The arrays are designed to produce a field effect similar to surgically implanted peripheral neurostimulators. The electrodes will be placed percutaneously in the external ear with the help of a transilluminator to visualize the neurovascular bundles. Three electrodes will be placed on the ventral and one on the dorsal aspect of the ear. The electrodes will be taped and secured behind the ear next to the generator itself which is secured to the skin with adhesive. The entire device may be covered by longer hair. The placement of the devices is within standard of care by properly trained medical doctors or pTRU nurses. Training of the MDs and pTRU nurses were performed by representatives of Innovative Health Solutions and certificates were issued upon completion. Research coordinators within the division of gastroenterology and neurology will store the devices as pre-packaged by manufacturer in boxes of 4 devices and label the devices with a serial number and patient ID number. A labeled folder for each patient with all clinical information and demographics needed for the entire study will also be kept with each subject package. The devices and folders will be stored in a locked office in

the gastroenterology division, only accessible by research coordinators. A research coordinator will bring each subject's numbered package to the research area (Translational Research Unit) when patient arrives. The package for the subject will be stored locked in the TRU until the subject finishes the 4 week therapy. The coordinator will ask the subject demographic questions and hand the device (numbered with serial # and patient ID only) to one of the certified MDs or pTRU nurses for placement. The devices will be "made to order" when requested by the PI and will be shipped packaged as above.

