- g. Syncope (fainting) - Rare (event rate 1% - < 5%)

Adverse effects to supporting personnel

- a. Skin piercing with percutaneous needles - Rare (event rate 1 % - < 5%)

**In our recently completed randomized trial of auricular neuro-stimulation for functional abdominal pain there were no significant or serious adverse events noted. Of 115 enrolled subjects, 10 reported side effects for following reasons, none of which were serious: ear discomfort n=6 (three active/three placebo device); adhesive allergy n=3 (one active/two placebo); syncope due to needle phobia n=1 (placebo).

Safety Monitoring Plan

All procedures will be performed by trained professionals within the standard of care under continuous medical supervision in the hospital setting (research unit). Side effects will be inquired about and documented every week during the study and at the post-study follow-up visit. If any serious harm or discomfort is identified by the subjects or the study personnel, the treatment will be discontinued. Any patient with worsening in symptoms

during the study will be able to drop out at any time and receive standard of care medical therapy. The skin of the external ear will be carefully disinfected to avoid any infection risks. Subjects will undergo vital sign screening before enrollment and vital sign assessment before EAD placement.

Safety Analysis Plan

There are no dangerous interventions related to this study, and the short study timeline allows for discontinuation of treatment when it is proven to be ineffective.

I. PROVISION FOR THE PROTECTION OF PRIVACY OF SUBJECTS AND TO MAINTAIN THE CONFIDENTIALITY OF DATA

All research projects that collect electronic data must use appropriate security measures to ensure that data is protected from theft or loss in order to prevent breaches of confidentiality. You must indicate what encryption tools (or why they are not necessary) from the options below. The IRB will not review this protocol unless you indicate the encryption tools being used to secure your research data. If you do not have encryption in place on your systems, please contact your Information Systems support to arrange for one of the encryptions options listed below.

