There are numerous, possible direct and long-term benefits to the subjects in this study. Our recently completed study of EAD in children with various functional abdominal pain disorders demonstrated improved pain, global well-being and functioning after only 3 weeks of therapy with effects sustained at 2 months follow-up (Accepted for publication: Kovacic, K Lacet GAstroenterology and Hepatology 2017). Since it is well documented that functional disability and quality of life is worse in adolescents with functional pain disorders with concurrent nausea than in those without nausea,(33, 34) and as many subjects in the above trial were noted to have improvement in concurrent nausea, we postulate that some of the improvement in well being and functioning may be due to reduction in nausea along with pain. There is now also mechanistic data through heart rate variability studies before and after therapy (unpublished data), suggesting the EAD acts through peripheral vagal nerve stimulation effects. Given the known vagal pathways involved in nausea and vomiting, we anticipate a reduction in nausea in subjects suffering from chronic functional nausea. Our prior studies on functional nausea show a high prevalence of anxiety and co-morbid GI symptoms including bloating, fullness and discomfort.(33, 35). Based on our prior data, we therefore also anticipate that concurrent symptoms such as bloating, post-prandial fullness, and anxiety may improve. Of 104 subjects analyzed, there were no significant side effects reported other than mild ear discomfort (n=6; n=3 in active and n=3 in placebo arm), adhesive allergy (n=3), and one subject with syncope due to needle phobia (placebo arm). Adolescents suffering from functional GI disorders thus have the opportunity to benefit from a non-pharmacological and non-invasive therapy without the adverse effects of pharmacological agents. The results of this study may provide important insights to the medical field regarding a poorly characterized group of patients and the underlying mechanisms.

L. STOPPING POINTS THAT WOULD NOT ALLOW THE STUDY TO CONTINUE AS PROPOSED

Stopping points for the study include unanticipated adverse events, and inability to obtain enough data or patients/caregivers electing to discontinue the study.

Reporting Adverse Events and Unanticipated Problems

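### Does the 1% to under 5% risk label for neuro-stimulation conflict with the 10 of 115 side effects reported from the team's earlier trial?

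*Combined protocol and SAP*

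**What the plan says.** Section H (Neuro-stimulation) opens its risk list with the line "Overall risks/ discomforts involved are very minimal – Rare (event rate 1% - < 5" per cent. Items a to g below it carry the same label. So does the staff risk that follows: "Skin piercing with percutaneous needles - Rare (event rate 1 % - < 5" per cent. None of these lines gives a denominator or a source.

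The note directly after the list reports the earlier trial: "Of 115 enrolled subjects, 10 reported side effects for following reasons, none of which were serious: ear discomfort n=6 (three active/three placebo device"), then "adhesive allergy n=3 (one active/two placebo); syncope due to needle phobia n=1 (placebo"). Section K repeats these counts, but for 104 subjects analysed instead of 115 enrolled. The size of each arm is not given in either place.

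Each subject in the present study has four placements (Table 1, visits 1 to 4). For visits 2 and 3, section D says "EAD will be changed and a new one will be placed", and section F describes devices "pre-packaged by manufacturer in boxes of 4 devices". A history of adhesive allergy is an exclusion (section D).

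**The concern.** A parent or ethics reviewer would probably take the overall line as the chance that a child has some side effect. On that reading the observed figure, 8.7%, is well above the label's 5% ceiling, and both stand in the same section. Changing the denominator to 104 makes the gap larger.

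The unit matters. If the label is per placement, a rate of 1% to under 5% becomes, over four independent placements, 1 − 0.99^4 = 3.9% to 1 − 0.95^4 = 18.5% per subject. The study enrols adolescents and is classed in section G as greater than minimal risk. An understated summary figure could mislead those who weigh risk against benefit.

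**Working it through.** **Inputs.** From the note in section H: ear discomfort 6 (3 active, 3 placebo), adhesive allergy 3 (1 active, 2 placebo), syncope 1 (placebo), 115 enrolled. From section K: 104 analysed. Assumptions, because the document is silent: active-arm size; one device per week in the earlier trial; one event per affected subject; 3 or 4 placements per subject. The last rests on section A, "4 weeks of auricular neuro-stimulation with an Electro Auricular Device (EAD) improves pain and functionality", and section K, "demonstrated improved pain, global well-being and functioning after only 3 weeks of therapy".

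**The plan's own figure.** The 1% to under 5% label has no stated derivation, so it cannot be reproduced. The counts do close: 6 + 3 + 1 = 10, and 4 active + 6 placebo = 10.

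**Reading 1: any side effect, per subject** (x/n, exact 95% interval where shown)

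| Set | x/n | Rate |
|---|---|---|
| Pooled, enrolled | 10/115 | 8.7% (4.2% to 15.4%) |
| Pooled, analysed | 10/104 | 9.6% (4.7% to 17.0%) |
| Pooled, without adhesive allergy | 7/115 | 6.1% (2.5% to 12.1%) |
| Active only, 58 assumed | 4/58 | 6.9% (1.9% to 16.7%) |
| Active, without adhesive allergy, 58 assumed | 3/58 | 5.2% (1.1% to 14.4%) |

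Every point estimate exceeds 5% and every lower limit is below it. If the true per-subject rate were 5%, the chance of 10 or more in 115 would be 0.063; of 4 or more in 58, 0.33. The last row is closest to the present study, which uses active devices and excludes adhesive allergy. It falls below 5% once the active arm has 61 subjects (3/61 = 4.9%), which is 61/115 = 53% of those enrolled. The row with all four active events would need 81 (4/81 = 4.9%), or 70% of those enrolled.

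**Reading 2: per placement**

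- Pooled: 10/(115 × 3) = 10/345 = 2.9%; 10/(115 × 4) = 10/460 = 2.2%.
- Active, 58 assumed: 4/174 = 2.3%; 4/232 = 1.7%.

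All lie inside the label.

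**Reading 3: a frequency class for each risk.** Seven items each at only 1%, if independent, would give 1 − 0.99^7 = 6.8% for any of them. The overall line therefore cannot easily be a cumulative incidence while every item carries the same label. By type the earlier trial gives:

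- adhesive allergy 3/115 = 2.6%;
- syncope 1/115 = 0.9%, just below the class;
- ear discomfort 6/115 = 5.2% (1.9% to 11.0%), just above it, though the protocol spreads discomfort over items a, b and d.

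The label on staff needle injuries, where trial subjects cannot be the unit, also suggests a stock class term.

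**Consequence.** With 7 subjects, the expected number with a side effect is 7 × 10/115 = 0.61 at the observed pooled rate, against 7 × 0.05 = 0.35 at the label's upper end. The safety analysis in section H is descriptive. The stopping points and reporting rules in section L contain no rate threshold.

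**The case for a change.** The strongest case for a change is that this is the summary risk line of a paediatric device study, that it has no unit, and that on the reading a lay reader would choose it is below the team's own observed proportion. Removing adhesive allergy does not bring the pooled figure under 5%, and neither does restricting to active devices under an equal split. The counts lie nearby, but nothing connects them to the label. Correcting it would take one line and one arm size from the team's own trial.

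Much of this stands. The unit and source are missing, the two denominators (115 and 104) are not explained, and the arithmetic is right. What does not stand is the step from a missing unit to an inconsistency. Two other readings fit the label about as well or better, and a true per-subject rate above 5% is not shown. The headline 8.7% is also not the risk that participants here face: 6 of the 10 events were on placebo devices and 3 of the 10 were adhesive allergies. The 18.5% figure needs the top of the label, a per-placement unit and independence all together, and no data in the document support that combination.

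**Conclusion.** No change to the plan follows. The overall line is loosely worded: it conflicts with the earlier trial's pooled 8.7% only if it means any side effect per subject. It agrees with the data per placement (2.2% to 2.9%, on an assumed 3 to 4 placements and one event per affected subject) and broadly as a class label for each risk, with ear discomfort marginal at 5.2%. For active devices without adhesive allergy, the answer turns on an arm size that the document does not give.

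A reader who wants the per-subject risk can take it from the counts by event and device printed directly under the list, which also say that none were serious. Stating the unit would tidy the text, but it would mostly move those counts up a few lines. The design, the descriptive safety summary, the section L rules and the section G risk category would all be the same.
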